## 1.2.1. Study Rationale

Liafensine has been tested in 11 Phase 1 studies, and 3 Phase 2b studies (including one rollover study). In the Phase 1 studies, single doses of up to 5 mg, and multiple doses of up to 4 mg liafensine were found to be generally safe and well tolerated. The pharmacokinetic (PK) profile of liafensine was compatible with once-daily (QD) dosing, supporting the potential for liafensine to have low potential for discontinuation symptoms. In the Phase 2b studies, patients who did not experience adequate response to either duloxetine (Study CN162006), or duloxetine or escitalopram (Study CN162007), were randomized to receive either liafensine or duloxetine (CN162006), or duloxetine or escitalopram (CN162007), for 6 weeks. In Study CN162006, a flexible dose of liafensine was used (0.5-2 mg QD). In Study CN162007, several fixed dosage levels of liafensine were used (0.25, 0.5, 1, and 2 mg OD). In these Phase 2b studies, liafensine was found to be generally safe and well tolerated. In Study CN162006, the most common adverse events (AEs) reported by at least 5% of patients treated with liafensine were headache (7.0%), nausea (7.0%), constipation (5.3%), and anxiety (5.3%). In Study CN162007, the most common AEs reported by at least 5% of patients treated with any dose of liafensine were headache (14.3%), nausea (12.0%), nasopharyngitis (8.8%), upper respiratory tract infection (8.0%), dry mouth (8.0%), constipation (7.7%), dizziness (7.0%), diarrhea (5.5%), fatigue (5.9%), and urinary tract infection (5.5%).

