## 8.3.4. Safety Analyses

The safety analyses will be conducted in the safety population, which includes all randomized patients who have received at least one dose of study drug. The safety population will be analyzed by the actual treatment received regardless of treatment randomized.

Adverse events will be coded using the current version of the Medical Dictionary for Regulatory Activities (MedDRA) classification system. Listings will include the verbatim term, preferred term, and system organ class. The incidence and severity of treatment-emergent adverse events (TEAEs) will be summarized by treatment. Vital signs including supine (after at least 5 min rest) and standing (after 1 min and 3 min standing), blood pressure and heart rate and heart rate, weight, ECG, clinical laboratory evaluation, DESS scale, and C-SSRS data will be summarized with descriptive statistics, by visit and by treatment.

Safety and tolerability data will be summarized descriptively, including tables, listings, and graphs, as appropriate. Unless otherwise stated, descriptive summary statistics for continuous variables will include number (N), mean (ie, arithmetic mean), standard deviation (SD), minimum, median, and maximum. Descriptive summary statistics for categorical data will include frequency and proportion.

All data will be presented by treatment regimen.

Individual data for vital signs including supine (after at least 5 min rest) and standing (after 1 min and 3 min standing), blood pressure and heart rate, weight, clinical laboratory measures, and ECG assessments will be listed and summarized for any potentially clinically important (PCI) values according to predetermined PCI criteria.

There will be no imputation (substitution) for missing data unless explicitly specified otherwise in this protocol or in the statistical analysis plan.

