2. STUDY DESIGN

2.1. Design Overview

This study will be conducted as a multicenter, randomized, double-blind, placebo-controlled Phase 2b trial to assess the efficacy, safety, tolerability, and PK of liafensine. The study includes an up to 21-day screening period (the screening period may exceed 21 days if a prolonged washout is required).

Approximately 180 patients with TRD who meet all eligibility criteria will be randomized in a 1:1:1 ratio to receive either placebo QD, liafensine 1 mg QD, or liafensine 2 mg QD for 6 weeks. Approximately 150 randomized patients will be genotype GG for DGM4 (DGM4-positive) and approximately 30 randomized patients will be genotype AA or AG for DGM4 (DGM4-negative). DGM4 status (positive vs negative) of randomized patients will be blinded to the sites, patients, and sponsor. An interactive response technology (IRT) system will be used for blinding to DGM4 status, and to achieve the correct randomization ratio of DGM4-positive:DGM4-negative patients by randomly excluding most screened DGM4-negative patients (~80%). Randomization will be stratified by DGM4 status (positive vs negative) and region (North America vs Other). Patients who complete the study or discontinue after randomization will have 2 post-study follow-up visits (14 days after the last administered dose of study drug, and 28 days after the last administered dose of study drug); the 2nd follow-up visit will be conducted via phone call.

The overall study design is shown in Figure 1.

Figure 1. Study Design

Abbreviations: ATRQ = Antidepressant Treatment Response Questionnaire; DGM4 = Denovo Genomic Marker 4; HAMD-17 = Hamilton Depression Rating Scale - 17 Item; QD = once daily; R = randomization.

Patients will be randomly assigned through an IRT system in a 1:1:1 ratio to receive either placebo QD, liafensine 1 mg QD, or liafensine 2 mg QD for 6 weeks.

Randomization Phase:

Placebo QD

• Day 1 through Day 42: two placebo tablets QD

Liafensine 1 mg QD

• Day 1 through Day 42: one 1 mg liafensine tablet and one matching placebo tablet QD

Liafensine 2 mg QD

- Day 1 through Day 7: one 1 mg liafensine tablet and one matching placebo tablet QD
- Day 8 through Day 42: two 1 mg liafensine tablets QD

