3.8.6. Discontinuation-Emergent Signs and Symptoms Scale

Discontinuation-Emergent Signs and Symptoms Scale (DESS) is used to monitor patients for discontinuation symptoms (Rosenbaum 1998). It includes 43 signs or symptoms for which the patient indicates whether there has been any change since their last visit – indicating new symptom, old symptom but worse, old symptom but improved, old symptom but unchanged, symptom not present. The DESS total score on a given day is calculated as the count of items with new symptoms or old symptoms but worse over all 43 items. For missing items, it will be imputed as the average from the non-missing items. The total score can range from 0 to 43. The number and proportion of subjects with the sum of zero, 1, 2, 3, and ≥ 4 will be presented each day and by the treatment arm. Treatment comparison will be performed each day from Day 1 to Day 14 using the Cochran-Mantel-Haenszel (CMH) test stratified by region and biomarker status. The average DESS total score over the assessment period will be calculated for each subject and compared between treatment group using the Wilcoxon rank-sum test.

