5.5.3. Vital Signs

Vital signs will include measurement of blood pressure (BP) and heart rate (HR): supine (after at least 5-min rest) and standing (after1-min and 3-min standing).

Actual value of BP and HR, between supine and standing (after 1-min and 3-min standing) at each visit (timepoint if applicable) will be presented using descriptive statistics by treatment group. A figure with the mean (\pm SD) of vital sign parameters by visit will be displayed.

Number of subjects with changes in HR (> 20 and > 30) will be presented at baseline and each post-baseline visit. The risk difference between treatment arms vs placebo, and 95% confidence interval will be calculated.

A separate table with a decrease in systolic BP > 20 mmHg, or diastolic > 10 mmHg on standing from supine position will be presented at baseline and each post-baseline visit. The risk difference between treatment arms vs placebo, and 95% confidence interval will be calculated.

Percentage of patients with maximum systolic BP by category of BP post-baseline (< 90, \geq 90, \geq 120, \geq 140, \geq 160, and \geq 180) will be presented.

Percentage of patients with maximum diastolic BP by category of BP post-baseline (< 60, > 60, > 90, > 110, and > 120) will be presented.

All vital signs data will be presented in a data listing.

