5.5.4. DESS scale and C-SSRS data

Discontinuation-Emergent Signs and Symptoms scale and C-SSRS data will be summarized by descriptive statistics at each visit and by treatment group unless otherwise specified. Change from baseline at each visit will be presented using descriptive statistics by treatment group for C-SSRS. Please see Section 3.8.6 for details on DESS.

All DESS scale and C-SSRS data will be presented in a data listing.

5.5.5. 12-Lead Electrocardiograms

ECG parameters (Heart Rate, RR interval, QRS Duration, QT Interval, QTcF) will be assessed according to the schedule of assessments in Table 1 of the protocol.

12-lead ECG recordings will be performed in triplicate (at approximately 1-min intervals between each of the three recordings) at baseline, and single ECG for rest of visits.

QT corrected by Fridericia's formula is recommended: $QTcF = QT/RR^{0.33}$.

Actual value, change from baseline, and percent change from baseline at each visit (timepoint if applicable) will be presented using descriptive statistics by treatment group.

Shift of ECG overall interpretation from baseline to end of treatment visit will be prepared with number and percentage of subjects being reported with Normal, Abnormal, Abnormal Clinically Significant, and Not Done.

The QTcF interval will be summarized by the frequencies of subjects with absolute value and/or change from baseline using the criteria identified below:

- <450
- \geq 450 to < 480
- ≥ 480 to < 500
- ≥ 500
- <30 increases from baseline
- 30 to ≤ 60 increases from baseline
- > 60 increases from baseline

Subjects with abnormal ECG results, regardless of clinical significance, will be identified in data listings with flags for abnormalities.

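### Discontinuation symptoms (DESS) are compared with placebo by significance tests alone, so the planned output cannot show how large an excess the data allow

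*SAP*

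**What the plan says.** DESS is a listed safety endpoint (Protocol 2.2.3, SAP 1.2.2), completed daily by the patient for 14 days after the last dose (Protocol Table 1, note m).

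SAP 3.8.6 plans three outputs:

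- A daily table, split by arm: "The number and proportion of subjects with the sum of zero, 1, 2, 3, and ≥ 4 will be presented each day and by the" …
- A daily comparison: "Treatment comparison will be performed each day from Day 1 to Day 14 using the Cochran-Mantel-Haenszel (CMH) test stratified by region and biomarker status".
- A comparison of each patient's average score over the period, "compared between treatment group using the Wilcoxon rank-sum test".

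SAP 5.5.4 adds: "Discontinuation-Emergent Signs and Symptoms scale and C-SSRS data will be summarized by descriptive statistics at each visit and by treatment group unless otherwise specified". It refers back to 3.8.6 for detail. Neither section asks for a between-arm difference, odds ratio, location shift or confidence interval.

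For liver thresholds (SAP 5.5.2) and for heart-rate and orthostatic blood-pressure changes (SAP 5.5.3), the same plan states: "The risk difference between treatment arms vs placebo, and 95% confidence interval will be calculated".

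The protocol planned no DESS tests. In its section 8.3.4, "DESS scale, and C-SSRS data will be summarized with descriptive statistics, by visit and by treatment". The SAP's list of changes from the protocol (section 6, Table 4) does not mention the added tests. The alpha rule in SAP 3.7 covers efficacy endpoints only, so the DESS tests have no stated level, sidedness or multiplicity rule.

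**The concern.** The safety question is whether stopping liafensine produces more discontinuation symptoms than stopping placebo, and by how much. The protocol's background expects little: the pharmacokinetic profile is described as "supporting the potential for liafensine to have low potential for discontinuation symptoms". DESS is the instrument chosen to look at this directly.

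A p-value does not answer the question in either direction. A non-significant test at this sample size is compatible with a sizeable excess, and the planned tables give no upper limit. An isolated significant day among 14 unadjusted tests is compatible with no effect at all. The reader of the study report would have per-arm proportions and a column of p-values, but no statement of precision. The SAP supplies that precision for other safety measures.

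**Working it through.** **Inputs from the documents.** "Approximately 180 patients with TRD who meet all eligibility criteria will be randomized in a 1:1:1 ratio" (SAP 2.1), so 180/3 = 60 per arm with both biomarker groups included; 14 daily tests; top tabulated category DESS of 4 or more (SAP 3.8.6).

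**Assumptions.** The documents give no DESS rate, relevant difference, alpha or allowance for missing diaries. I assume 2-sided 0.05, all 60 per arm evaluable, and the rates shown below.

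**1. The plan's only power figure.** For the primary endpoint (SAP 2.3: difference 4.5, SD 9, pooled doses 2:1 against placebo), n per arm = (1.960 + 0.842)² × 81 × 1.5 / 4.5² = 47.1. At 47 per arm, power is 79.9%. The stated 47 reproduces. It says nothing about DESS.

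**2. Power of one daily test, one dose vs placebo.** For DESS of 4 or more at 10% vs 20%:

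- null SE = √(2 × 0.15 × 0.85 / 60) = 0.0652
- alternative SE = √((0.09 + 0.16) / 60) = 0.0645
- power = Φ((0.10 − 1.96 × 0.0652) / 0.0645) = Φ(−0.43) = 33%

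Other assumed rates, same formula:

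| Placebo vs dose | Power, one dose (60 vs 60) | Power, pooled (120 vs 60) |
|---|---|---|
| 10% vs 20% | 33% | 39% |
| 10% vs 25% | 58% | 68% |
| 10% vs 30% | 79% | 89% |
| 20% vs 30% | 24% | 29% |

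These use a two-category test. A simulated five-category CMH test gives about the same for 10% vs 20% (31% per dose) and 10% vs 30% (80%).

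**3. Power of the Wilcoxon test on the average.** For a shift of 0.5 SD and relative efficiency 0.955: Φ(0.5 × √(0.955 × 60 / 2) − 1.96) = Φ(0.72) = 76% per dose.

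**4. False alarms with no effect.** If the 14 tests were independent, 1 − 0.95¹⁴ = 51%. Daily scores within a patient are correlated, which lowers this:

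- Test statistics simulated with AR(1) correlation 0.5, 0.7 and 0.9: at least one significant day in about 46%, 40% and 24% of trials (pooled contrast).
- Binary daily outcomes at 10% with latent AR(1) correlation 0.5 to 0.9, one dose vs placebo: about 38-51%.

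The overall range is about 24-51% for a single contrast.

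**5. What a confidence interval would add.** Take 13/60 on a dose and 6/60 on placebo.

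- Test: pooled rate 19/120 = 0.158; z = 0.1167 / √(0.158 × 0.842 × 2/60) = 1.75; p = 0.08.
- 95% CI: 0.1167 ± 1.96 × √(0.09/60 + 0.170/60) = 0.117 ± 0.129, or −1 to +25 points.

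The planned output would show the p-value and not the 25-point upper limit. With equal observed rates, the half-width is 1.96 × √(p(1 − p)(1/60 + 1/n)), with n = 60 for one dose and 120 pooled:

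| Common rate | One dose | Pooled |
|---|---|---|
| 10% | ±11 points | ±9 points |
| 20% | ±14 points | ±12 points |
| 30% | ±16 points | ±14 points |

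**The case against.** **A null result will be taken as no withdrawal effect.** A reader might infer this from the background sentence on low potential for discontinuation symptoms. The documents do not support it. That sentence draws on the pharmacokinetics of earlier studies. No section sets a hypothesis, margin or reading rule for DESS.

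**The plan would usually miss a relevant harm.** A reader might infer this from the single-test power. It does not follow for the set of tests. If an excess of 10% vs 20% persisted on all 14 days, no day would be significant in only about 2-15% of trials (one dose, 60 per arm, latent AR(1) correlation 0.5-0.9); a constant latent correlation of 0.5-0.8 gives 7-19%. The single-test figures also move with assumed rates, alpha and evaluable numbers, so no one miss rate can be attributed to the plan. What remains is that the same set of tests often flags a day when nothing is going on, and that no p-value gives the size of an excess.

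**The data are displayed.** Daily proportions by arm are tabulated, so a crude difference, and with some work its interval, can be computed from the counts. Adverse events are also counted as treatment-emergent to 30 days after the last dose (SAP 5.5.1). Both points are fair. The plan still does not report the precision of any DESS difference.

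**This is a secondary safety scale in a Phase 2b trial, and the SAP already does more than the protocol asked.** This is true, and it limits the weight of the point. But what was added is tests, without the estimates the SAP uses for other safety measures.

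**Conclusion.** The point holds as a gap in reporting. The planned between-arm DESS comparisons are 14 unadjusted daily CMH tests and one Wilcoxon test, with no difference from placebo, confidence interval or multiplicity rule. This departs from the SAP's own format for liver tests and vital signs. The p-values cannot show how large an excess of discontinuation symptoms the data allow, and at about 60 per arm that could be large: a non-significant comparison can leave an upper limit near +25 points.

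That the comparisons are tests only is read directly from the SAP. The power and false-alarm figures rest on assumed rates, 2-sided 0.05, full diary completion and assumed day-to-day correlation; missing diaries would lower power. The recommendation does not depend on any of them. No primary or key secondary conclusion is affected. I would class this as a cheap improvement.

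**What to change.** In SAP 3.8.6 and 5.5.4, for 1 mg, 2 mg and pooled doses vs placebo:

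1. Add the risk difference with 95% CI for DESS total of 4 or more at any time in the 14 days, stratified by region and biomarker status where stratum sizes allow. The cut-off is the SAP's top tabulated category, not a validated threshold, and should be described that way.
2. Add the Hodges-Lehmann difference with 95% CI beside the Wilcoxon p-value for the average score.
3. Label the 14 daily comparisons descriptive.
4. State that a non-significant test will not be reported as absence of excess discontinuation symptoms, and that the confidence interval will be reported instead. A decision rule on the upper limit would need a margin, which the documents do not provide, so none is proposed.
5. List the DESS analyses in SAP Table 4 as an addition to the descriptive summaries in the protocol.

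The cost is some SAP wording and a few table rows, with no new data or patients. The intervals will be visibly wide, which is an accurate picture of what about 60 patients per arm can show.

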2.3. Sample Size Calculation

Eligible patients will be randomized 1:1:1 to receive placebo QD, liafensine 1 mg QD, or liafensine 2 mg QD. The primary analysis is to assess treatment difference in MADRS total score change from baseline (Visit 3, Day -1) to Visit 7 (Day 42), between the combined liafensine 1 mg QD and 2 mg QD doses vs placebo, in DGM4-positive patients. A sample size of 47 randomized DGM4-positive patients per arm is sufficient to detect a 4.5-unit difference between the combined liafensine 1 mg QD and 2 mg QD and 2 mg QD and 2 mg QD treatment groups and the placebo treatment group in the change in MADRS total score from baseline to Day 42 with 80% power at the 2-sided 0.05 alpha level, assuming a standard deviation (SD) of 9 units.

To compensate for potential loss of power due to randomized patients who do not take at least one dose of study drug or who do not have a post-randomization efficacy evaluation (~5%), a total of approximately 150 DGM4-positive patients (50 DGM4-positive patients per arm) will be randomized.

To examine trend in the total patient population and in the subgroup of DGM4-negative patients in order to evaluate DGM4 as a potential biomarker for predicting response to liafensine, approximately 20% additional DGM4-negative patients (10 per arm, total 30) will also be randomized. The sample size of 30 randomized patients in the DGM4-negative group is not estimated based on formal statistics in terms of power and alpha level.

Sample size re-estimation may be conducted if the percentage of missing data at Day 42 visit is higher than expected and/or if the observed variance is higher than the one assumed in the sample size estimation.

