3.6. Stratified Analysis

Efficacy analyses will be stratified by biomarker status and region. Details are presented under the analysis for each endpoint.

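### The overall DESS comparison in SAP 3.8.6 is unstratified although randomisation and the daily DESS tests are stratified; it is valid, but loses power if region or DGM4 status predicts DESS

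*SAP*

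**What the plan says.** SAP 3.8.6 plans two kinds of DESS comparison, one directly after the other.

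- **Daily, Day 1 to Day 14:** treatment groups are compared "using the Cochran-Mantel-Haenszel (CMH) test stratified by region and biomarker status".
- **Overall:** each subject's average total score is "compared between treatment group using the Wilcoxon rank-sum test". No strata are named, and the pairs of groups to be compared are not listed.

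SAP 2.1 and Protocol 5.5 stratify randomisation by DGM4 status and by region (North America against Other), which gives four strata. On their sizes SAP 2.1 says: "Approximately 150 randomized patients will be genotype GG for DGM4 (DGM4-positive) and approximately 30 randomized patients will be genotype AA or AG". The regional split is not given.

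The general rule in SAP 3.6 covers efficacy only: "Efficacy analyses will be stratified by biomarker status and region". DESS is listed as a safety endpoint (SAP 1.2.2). Protocol 8.3.4 plans no DESS test at all: "DESS scale, and C-SSRS data will be summarized with descriptive statistics, by visit and by treatment". SAP 5.5.4 refers back to 3.8.6 for the DESS detail.

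**The concern.** When patients are randomised within strata, the arms are balanced on those factors by design. A rank test that ignores the strata still counts the between-stratum spread in its variance. If a stratum factor predicts the outcome, that variance is too large, the real false-positive rate falls below nominal, and power is lost.

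DESS is a patient-completed symptom count, so its level could plausibly differ by region. The average is the only planned test that summarises discontinuation symptoms over the whole assessment period; the alternative is 14 separate daily tests. The protocol rationale (Synopsis and 1.2.1) regards the pharmacokinetic profile as pointing to a low potential for such symptoms. A non-significant overall result could be read as support for that view, so any lost power would err in the drug's favour. The SAP gives no reason for treating the two tests differently.

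**Working it through.** **1. The plan's own figures.** No DESS effect size, variance, alpha or power is stated. The only power figure is for MADRS (SAP 2.3: 47 per arm, difference 4.5, SD 9, 80% power, two-sided 0.05). With 2:1 pooled allocation the placebo number is (1 + 1/2) × (1.960 + 0.842)² × (9/4.5)² = 1.5 × 7.85 × 4 = 47.1, or 48 rounded up; 47 gives 79.9% power. The figure reproduces but has no bearing on DESS.

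**2. Inputs for DESS.**

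- From the documents: 1:1:1 allocation; about 150 DGM4-positive and 30 DGM4-negative patients, so 50 + 10 = 60 per arm and 120 against 60 when the doses are pooled; four strata.
- Assumed: a 14-day mean of Poisson counts with a gamma patient effect (shape 1, placebo mean 1.5); active/placebo ratio 1.6; two-sided 0.05; North America share p; ratio R of average DESS between regions; no DGM4 effect unless stated.

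**3. Approximation for the false-positive rate.** Let h be the share of rank variance lying between strata. With allocation balanced within strata, the true null variance is about (1 − h) times the one the ordinary test uses, so

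size ≈ 2Φ(−1.96/√(1 − h)).

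Ranks scaled to 0-1 have variance 1/12. With P the chance that a patient in the higher-scoring region outscores one in the other, the regional mean ranks differ by P − 1/2, so h = 12p(1 − p)(P − 1/2)². For gamma shape 1, ignoring day-to-day Poisson noise, P = R/(R + 1).

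Example, p = 0.5 and R = 3: P = 0.75; h = 12 × 0.25 × 0.0625 = 0.1875; 1.96/√0.8125 = 2.174; size = 3.0%.

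**4. Simulation.** 10,000 trials per setting, pooled doses against placebo, ordinary rank-sum test (U) against van Elteren with stratum weights 1/(n + 1) (S). The Monte Carlo standard error of a 5% rate is √(0.05 × 0.95/10,000) = 0.2 points.

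| p | R | Size U, formula | Size U / S, simulated | Power U / S | Loss (points) |
|---|---|---|---|---|---|
| 50% | 1 | 5.0% | 4.9 / 4.9% | 70.8 / 69.9% | −0.9 |
| 50% | 1.5 | 4.7% | 4.6 / 4.9% | 68.8 / 69.8% | 1.0 |
| 50% | 2 | 4.1% | 3.9 / 4.8% | 66.6 / 70.5% | 3.9 |
| 50% | 3 | 3.0% | 2.7 / 4.5% | 61.6 / 71.0% | 9.4 |
| 70% | 1 | 5.0% | 4.8 / 5.0% | 71.2 / 70.8% | −0.4 |
| 70% | 1.5 | 4.7% | 4.5 / 4.9% | 70.5 / 70.7% | 0.2 |
| 70% | 2 | 4.2% | 4.5 / 4.9% | 67.2 / 69.8% | 2.6 |
| 70% | 3 | 3.3% | 3.4 / 5.3% | 63.1 / 70.8% | 7.7 |
| 90% | 1 | 5.0% | 4.8 / 4.8% | 70.4 / 69.6% | −0.8 |
| 90% | 1.5 | 4.9% | 4.5 / 4.5% | 71.3 / 71.2% | −0.1 |
| 90% | 2 | 4.7% | 4.6 / 5.0% | 70.6 / 71.3% | 0.7 |
| 90% | 3 | 4.2% | 4.1 / 4.8% | 68.4 / 71.0% | 2.6 |

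Formula and simulation agree closely. The unstratified test never exceeded the nominal rate.

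**5. Sensitivity.**

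- One dose against placebo (60 against 60, p = 50%, R = 3): power 49% against 58%. With less between-patient spread (gamma shape 2): 76% against 89%, a loss of 13 points.
- Region and DGM4 both at a ratio of 3: loss 8-14 points across p = 50-90%.
- Region at 5 with DGM4 at 2: loss 8-22 points. Nothing in the documents suggests effects this large.

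**The case against.** The strongest reply is that no rule is broken and no harm is shown. SAP 3.6 limits stratification to efficacy. The protocol plans DESS as descriptive, so the Wilcoxon test is an addition with no alpha or decision rule attached. Other safety comparisons, such as the risk differences in SAP 5.5.2 and 5.5.3, also name no strata. The documents contain no DESS data by region or genotype, so the loss may be nil; with a 90% North America share it is under 1 point even at a twofold regional difference. The 14 daily stratified tests, the daily category tables and the listings all remain.

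Most of this stands, and it keeps the point small. It does not explain the inconsistency: the sponsor already chose to stratify the daily tests of this same safety endpoint, so an efficacy-only rule cannot be why the overall test differs.

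Three stronger readings are tempting and should not be drawn:

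- **That the test is conservative as a matter of fact.** This needs region or DGM4 status to predict DESS, which is not documented. Without that, size is nominal and the plain test is slightly the more powerful.
- **That the plan will miss withdrawal effects.** The daily stratified tests and tables are still there, and no stated conclusion rests on the overall p-value alone.
- **That the SAP breaches its own stratification rule.** That rule does not extend to safety endpoints.

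**Conclusion.** The point holds as a minor, conditional one. The overall DESS test is valid as written but does not match the randomisation or its companion daily tests. It gives up power to the extent that the strata predict DESS.

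Under the stated assumptions, with a North America share of 50-80%, the loss is about 1 point or less at a regional ratio of 1.5, about 2-4 points at 2 and about 5-10 points at 3. It can exceed that in single-dose comparisons with little between-patient spread, and it shrinks when one region dominates. If the strata are irrelevant, stratifying costs about 1 point. The DESS distribution, drug effect, regional split and regional ratio are all assumed; only the direction does not depend on their values. Neither the primary MADRS analysis nor its conclusion is touched.

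**What to change.** In SAP 3.8.6, replace the ordinary rank-sum test on the subject average with the stratified Wilcoxon (van Elteren) test, using region and DGM4 status as in the daily CMH tests. State that it is run for 1 mg, 2 mg and the pooled doses, each against placebo.

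Add a rule, fixed before unblinding, that region is pooled within DGM4-negative patients if a stratum is sparse or empty, and give the threshold. With about 10 DGM4-negative patients per arm, an even regional split leaves 5 per arm in each stratum, and a 90:10 split leaves 9 and 1. If the sponsor prefers to keep the unstratified test, one sentence giving the reason would settle the inconsistency.

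The cost is a phrase and a pooling rule in the SAP and a scoring option in the stratified CMH procedure already used in SAP 8.8 (modified ridit scores, with DGM4 status added as a stratum). No new data are needed.
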